7.1. Primary Outcome Measure

Estimated proportion of participants who died or had bleeding of WHO grade 2 or above during the first 30 days of the trial **from the first day of trial treatment**

A time-to-event analysis will be used to determine this proportion to ensure that all participants are included in the primary outcome analysis, not just those who are followed up for the full 30 days. Any participants lost to follow-up will be included in the analysis and censored at the time that they were lost.

7.2. Secondary Outcome Measures

7.2.1. Secondary Efficacy Outcomes

All measured during first 30 days of the trial, i.e. **from the first day of trial treatment**.

- Proportion of days with bleeding (WHO grade 2 or above)
- Time to first episode of bleeding of WHO grade 2 or greater
- Highest grade of bleeding a participant experiences
- Number of platelet transfusions/participant
- Number of red cell transfusions/participant
- Proportion of participants surviving up to 30 days without a platelet transfusion
- Proportion of participants surviving up to 30 days without a red cell transfusion
- Quality of life

7.2.2. Secondary Safety Outcomes

- Number of thrombotic events from first administration of trial treatment up to and including 120 days after the first dose of trial treatment is administered, per day at risk
- Number of participants developing Venous Occlusive Disease (VOD; Sinusoidal obstructive syndrome, SOS) within 60 days of first administration of trial treatment
- All-cause mortality during the first 30 days and the first 120 days after the first dose of trial treatment is administered
- Death due to thrombosis during the first 120 days after the first dose of trial treatment is administered
- Death due to bleeding during the first 30 days after the first dose of trial treatment is administered
- Number of serious adverse events from first administration of trial treatment until 60 days after the first dose of trial treatment is administered

7.2.3. Other outcomes

All measured during first 30 days of the trial, i.e. **from the first dose of trial treatment**

- Proportion of days with thrombocytopenia ($\leq 10 \times 10^9/L$, $\leq 30 \times 10^9/L$, $\leq 50 \times 10^9/L$)
- Proportion of days with fever (highest daily temperature $\geq 38.1^\circ\text{C}$) of days spent in hospital, up to study day 30
- Reasons for platelet and red cell transfusions

7.3. Sub-group analyses

Subgroup analyses will be performed for the primary outcome for the following variables in the main analysis:

- Country of participant (UK vs. Australia), if evidence of heterogeneity between UK and Australian participants is identified in the interim analysis
- Platelet count at consent ($\leq 30 \times 10^9/L$ vs. $> 30 \times 10^9/L$)
- Treatment compliance during first 30 days of the trial (withdrawal of consent for trial treatment vs. no withdrawal of consent)

8. Assessments and Follow-up

8.1. Trial Assessment Schedule

Please see study schedules Pages 13 & 14

8.2. Procedures for Assessing Efficacy

8.2.1. Bleeding Assessment

Bleeding assessment will commence when the participant is randomised and stopped when one of the following occurs:

- It has been 30 days since the trial treatment was commenced
- Or in those cases where trial treatment was *not* started, 30 days from platelet count $\leq 30 \times 10^9/L$ or the commencement of chemotherapy/stem cell conditioning therapy
- The participant dies.
- Participant withdraws his/her consent to having bleeding assessments performed.
- Site investigator withdraws the participant from all further study assessments.

Bleeding assessments will be conducted using a tool based upon that used in the recent TOPPS trial ([20](#)) and further developed by an international working group – the BEST collaborative ([46](#)). If a participant is an out-patient between day of randomisation and trial treatment starting they will be asked to inform the research team if they have had any bleeding at home. Simple guidance notes will be provided to assist with this.

Rates of recorded bleeding are known to vary considerably between trials. Reasons for this variability have been explored and published through a review organised by the BEST collaboration, and include different patient groups and bleeding definitions, and variable follow up periods ([39](#)).

In the TREATT trial, a number of measures will be taken to standardise documentation and recording of bleeding, including trained assessors, monitoring and education. In the recent TOPPS ([20](#)) trial, where completeness of bleeding outcome documentation was excellent, a bleeding assessment was completed on 93% (8405/9030) of days for patients in the no-prophylaxis group, and 97% (8733/8970) of days in the prophylaxis group. The majority of patients in both arms had bleeding information collected on each trial day (median no-prophylaxis 30 days (IQR 29 to 30); median prophylaxis 30 days (IQR 30 to 30)).

For inpatients, bleeding assessments will be performed using the bleeding assessment tool which includes a physical assessment of the participant, patient interview (if possible) and review of patient chart and laboratory data. Research staff will perform the physical assessment and interview before reviewing the participant's charts, medical notes and

laboratory data to allow an objective assessment. Research staff will perform the bleeding assessment at approximately the same time each day.

All participants who are discharged home before completion of the trial study period (30 days from commencement of the trial treatment) will be asked to complete a daily diary. Participants will be provided with clear guidance notes to assist them in self-assessment of bleeding. They will be asked to respond with a yes/no answer as to whether they have experienced any bleeding on that day.

If a participant reports no bleeding on their bleeding diary this will be recorded as a WHO grade 0 bleed. If the participant does report bleeding they are asked to consult with their haematology care team. If the clinical team consider the bleeding to be significant then the participant should be reviewed and a bleeding assessment will be conducted by a member of the research team. If the haematology team considers the bleeding to be clinically insignificant, this will be recorded as WHO grade 1

Additionally, all participants at home will be contacted by the local research staff on day 30 from first dose of the trial treatment to review the diary and confirm arrangements to collect all completed forms, which will be forwarded on to the data manager for entry into the trial database.

Local research staff completing the daily assessments will receive training and have guide notes to help them collect these data.

8.2.2. Assigning a grade to a bleed

Grade of bleed (WHO Grading System - see 20.2) will be assigned centrally by means of a computer algorithm at the time of analysis.

8.3. Procedures for Assessing Safety

8.3.1. Thrombotic Assessment

For in-patients, medical chart notes and imaging studies will be reviewed daily for documentation of any thrombotic events. For out-patients, the local research nurses will attempt to contact the participant directly, and if contact is not made, the participants' local physician / GP will be contacted.

Safety outcomes will include recording symptomatic thrombotic events that occur during the study period and up to 120 days (+/-7) after the first dose of the trial treatment is administered.

8.3.2. Interval Medical Events/Serious Adverse Events

A member of the research team will contact the participant in person or by telephone to ask them about any interval medical events or serious adverse events after discharge from hospital. If the research team are unable to contact the participant directly, their local physician/GP will be contacted.

8.4. Other Measurements

The following data will be collected:

Demographics and Medical History

This will include:

- Weight

- Height
- Date of birth
- Gender
- Ethnic origin
- Diagnosis (disease and type or treatment: i.e. chemotherapy or type of stem cell transplant)
- If receiving allogeneic transplant, whether HLA matched or mismatched
- Type and date of transplant or first day of other treatment
- Previous co-morbidities
- Renal impairment
- Previous fungal infection

Laboratory Studies (All study centres)

- Urine dipstick (at enrolment)
- Haemoglobin and platelet count, required daily when participant is an in-patient and 3 times a week, or as Standard of Care, when participant is an out-patient
- Coagulation profile (PT or INR), at randomisation.
- Serum creatinine (required at enrolment, randomisation, study days 1&2, and then 3 times a week on Monday, Wednesday and Friday, or as SOC, when participant is on trial treatment)
- Liver function tests including bilirubin and albumin required if VOD suspected / reported three times a week
- HLA antibody screen - required at enrolment, and repeated if a participant develops platelet refractoriness (defined as two sequential transfusions with a 24 hour platelet increment $<5 \times 10^9/L$)

Laboratory Studies (Selected study centres)

- Fibrinolysis assay (central/local lab) – sub-study
- C-reactive protein (CRP) (this is required daily when participant is an in-patient if it is measured routinely at the participating hospital)
- Immature platelet fraction (this is required daily when participant is an in-patient and at least 3 times per week, when participant is an out-patient)

Transfusions given during study (from enrolment to study day 30)

- Data on platelet, granulocyte or stem cell transfusion
 - Reason for transfusion (prophylaxis, invasive procedure, active bleeding, risk of significant bleeding, other)
- Data on red cell transfusions
 - Number of units transfused
 - Reason for transfusion (anaemia, active bleeding, other)

Fever

- Highest temperature within each 24 hour period (defined as 8am to 8am) when participant is an inpatient

Quality of Life Assessment

- Quality of life assessment (EQ5D & FACT-Th) at randomisation, day 12 (± 2) and day 30 (± 2). EQ-5D at day 120 (± 7).

Health economic analysis (from study day 1 to study day 120)

- Number of hospital admissions, and duration of stay
- Number of ITU admissions and duration of stay
- Number of day unit admissions

- Number of hospital outpatient visits
- Yes/No question as to whether the participant has had any further treatment for their haematological malignancy
- Whether the participant has active haematological disease at day 120

8.5. Loss to Follow-Up

If the local research team are unable to contact a participant to obtain follow-up data, consent will be obtained on enrolment to the trial to contact their family physician / General Practitioner.

- **Death**

Data will be recorded on all-cause mortality, mortality due to bleeding and mortality due to thrombosis.

- **Discontinuation of Trial treatment**

Participants are free to stop the trial treatment at any time. The date will be recorded, along with the reason, on a designated trial treatment discontinuation form. In the event of the participant stopping the trial treatment, the participant will still be followed for all trial outcomes according to the protocol, unless they have specifically withdrawn consent for further data collection.

- **Withdrawals**

Participants may withdraw or be withdrawn from the trial at any time for any of the following reasons:

1. Participant withdraws consent
2. Investigator withdraws participant from the trial
3. Death

- **End of trial for each participant**

The trial end date for each participant will be the date of the last telephone call or outpatient visit at study day 120.

8.6. Trial Closure

The trial will be closed to recruitment when the required number of participants has been recruited and the last participant has completed the trial intervention period (to Day 30).

9. Safety Reporting

The principles of ICH GCP require that both investigators and sponsors follow specific procedures when notifying and reporting adverse events or reactions in clinical trials. These procedures are described in this section.

In general, investigators should report adverse events as diseases or syndromes whenever possible, instead of reporting individual component symptoms, signs, laboratory abnormalities or sequelae.

9.1. Definitions of Adverse Events

The definitions to be applied to adverse events occurring during this trial are given in Table 9a below. When an adverse event occurs, the PI or delegate should first classify the event according to table 9a below. Events of interest and that require to be reported are any:

- Unexpected Adverse Reactions
- Serious Adverse Events

that occur during the trial period that are **not already listed as primary or secondary outcomes**. Any other adverse event does not need to be recorded.

Table 9a: Definitions

Term	Definition
Adverse Event (AE)	Any untoward medical occurrence affecting a trial participant during the course of a clinical trial and which does not necessarily have to have a causal relationship with participation in the research.
Adverse reaction to an investigational medicinal product (AR)	An adverse event when there is at least a possibility that it is causally linked to a trial drug or intervention.
Unexpected Adverse Reaction (UAR)	An unexpected adverse reaction is an AR in which the nature or severity of the reaction is not consistent with the known side effects of the trial drug or intervention. There need only be an index of suspicion that the event is a previously unreported reaction to a trial drug or intervention.
Serious Adverse Event (SAE) or serious adverse reaction (SAR)	Any adverse event (AE) or adverse reaction (AR) that meets any of the following criteria: 
 • results in death • is life-threatening • requires hospitalisation or prolongation of existing hospitalisation • results in persistent or significant disability or incapacity, results in a congenital anomaly/birth defect • any other adverse event that, based upon appropriate medical judgment, may jeopardise the subject's health and may require medical or surgical intervention to prevent one of the other outcomes listed in this definition
Suspected Unexpected Serious Adverse Reaction (SUSAR)	A suspected unexpected serious adverse reaction is an unexpected occurrence of a SAR; in which the nature or severity of the reaction is not consistent with the known side effects of the trial drug or intervention. There need only be an index of suspicion that the event is a previously unreported reaction to a trial drug or intervention.
Unanticipated problem involving risks to subjects or others (UP)	Any incident, experience, or outcome that meets all of the following criteria: 
 a. unexpected (in terms of nature, severity, or frequency) given (a) the research procedures that are described in the protocol-related documents, such as the REC-approved research protocol and informed consent document; and (b) the characteristics of the subject population being studied; b. related or possibly related to a subject's participation in the research; and c. suggests that the research places subjects or others at a greater risk of harm (including physical, psychological, economic, or social harm) related to the research than was previously known or recognised

Medical judgement should be exercised in deciding whether an AE is serious in other situations. Important AEs that are not immediately life-threatening or do not result in death or hospitalisation but may jeopardise the subject or may require intervention to prevent one of the other outcomes listed in the definition above, should also be considered serious.

9.2. Investigator Responsibilities

The Chief Investigator (CI) has overall responsibility for the conduct of the trial. As this is a multi-site trial, the Principal Investigator (PI) has responsibility for the research at their local

[figure not shown]
site and is responsible for informing the CTU of all reportable serious or unexpected adverse events or reactions that occur at their site following the flow chart and guidelines below.

9.2.1. Investigator Assessment of Adverse Events

Causality

The causality of all AEs should be assessed by the PI (or delegate) using table 9b below. There are 5 categories: unrelated, unlikely, possible, probable and definitely related.

Table 9b: Definitions of Causality

Relationship	Description
Unrelated	There is no evidence of any causal relationship
Unlikely	There is little evidence to suggest there is a causal relationship (e.g. the event did not occur within a reasonable time after administration of the trial treatment or intervention). There is another reasonable explanation for the event (e.g. the patient's clinical condition, other concomitant treatment).
Possible	There is some evidence to suggest a causal relationship (e.g. because the event occurs within a reasonable time after administration of the trial treatment or intervention). However, the influence of other factors may have contributed to the event (e.g. the patient's clinical condition, other concomitant treatments).
Probable	The evidence is clearly in favor of attributing the adverse reaction to the trial treatment or intervention

Definitely	There is conclusive evidence beyond reasonable doubt attributing the adverse reaction to the trial treatment or intervention.
-------------------	---

Seriousness

When an AE or AR occurs, the investigator responsible for the care of the patient must assess whether or not the event is serious using the definitions in Table 9a: definitions. If the event is serious and is on the list of expected events in section 9.1, then the details must be recorded on the SAE form within five working days. If the event is a SUSAR it must be recorded on the SAE form and sent to the CTU within 24 hours of becoming aware of it.

Expectedness

For all events and reactions, the Investigator must assess the expectedness. Please refer to the Investigator Brochure Section 8 for a list of expected serious adverse reactions to the trial treatment. This is the reference safety information for the trial.

Additional information on expected adverse reactions is available in Section 4.8 of the Summary of Product Characteristics (found in Section 16 of the Investigator Brochure) for a list of expected adverse reactions to the oral trial treatment and in Section 7 of the investigator brochure for the intravenous trial treatment.

9.3. Adverse Event Reporting

9.3.1. Adverse Events that Require Expedited Reporting (within 24 hours)

Any SAEs (related or unrelated) or unexpected (but not serious) adverse reactions must be reported within 24 hours of the PI becoming aware of the event, unless they have been specifically excluded from expedited reporting (see section 9.3.2).

9.3.2. Trial Specific Exceptions to Expedited SAE Notification (within 5 working days)

These are SAEs that are associated with the disease that the participants will be suffering from, and will not impact on the scientific interpretation of the results of the trial.

Due to the seriousness of the disease(s) the patients in this trial are suffering from, the following situations that fulfil the definition of an SAE are excluded from expedited notification, but should be recorded on the SAE form and reported within five working days:

- Elective hospitalisation to evaluate the treatment management plan for the patient's disorder, or for procedures
- Elective hospitalisation for pre-existing conditions that, in the investigator's opinion, have not been exacerbated by trial treatment
- Admission to the intensive care unit
- Severe sepsis
- Major organ dysfunction
- Any other serious event related to the underlying disease or medication used to treat the disease
- Death as a result of disease progression

Any event that does not meet the above definitions does not need to be recorded at all.

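### A listed serious event that is also a SUSAR has two site-reporting deadlines, 24 hours and five working days, and the protocol does not say which prevails

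*Protocol*

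**What the plan says.** The rules on how fast a site must report are spread over several parts of Protocol section 9.

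- **9.3.1 (general rule):** "Any SAEs (related or unrelated) or unexpected (but not serious) adverse reactions must be reported within 24 hours". The rule carries an override: "unless they have been specifically excluded from expedited reporting (see section 9.3.2".
- **9.3.2 (exceptions):** the section says that "the following situations that fulfil the definition of an SAE are excluded from expedited notification", and allows five working days for the report instead. The list includes "Admission to the intensive care unit", severe sepsis and major organ dysfunction, each without a qualifier.
- **9.3.3 (notification):** repeats five working days for any SAE excluded from expedited reporting. Separately, it asks for notification of a UAR within 24 hours and states no exclusion.
- **9.5 (boxed notice):** 24 hours unless the SAE has been excluded from expedited reporting.
- **9.2.1 (Seriousness):** "If the event is a SUSAR it must be recorded on the SAE form and sent to the CTU within 24 hours". The sentence before it gives five working days to a serious event that "is on the list of expected events in section 9.1".
- **9.1 (Table 9a):** "A suspected unexpected serious adverse reaction is an unexpected occurrence of a SAR". An index of suspicion is enough.

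**The concern.** The three bullets name events by clinical type. An ICU admission or organ failure can come from the malignancy, from its treatment or from the blinded trial drug, and the bullets do not distinguish these. The override in 9.3.1 is attached to a rule that already covers related and unrelated events, so a suspicion of drug causality does not by itself bring a listed event back to 24 hours.

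At stake is the speed at which a SUSAR reaches the CTU. Under 9.4 the CTU is responsible for reporting SUSARs to the regulators and ethics committees, and it cannot do so before the site has reported. Organ dysfunction is a relevant category here, because 6.2.5 names a risk of accumulation of tranexamic acid in renal insufficiency.

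**Working it through.** There is no figure in the plan to reproduce. The check is a comparison of the rules, applied to one type of event: a listed event (ICU admission, severe sepsis or major organ dysfunction) that the investigator suspects is related to trial treatment and that is unexpected.

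| Provision | Deadline for this event | Exception or precedence stated? |
|---|---|---|
| 9.3.1 | Defers to 9.3.2 | Exception for listed events; relatedness is not a condition |
| 9.3.2 | Five working days | No exception for suspected drug causality in these three bullets |
| 9.3.3, SAE text | Five working days | None |
| 9.5 notice | Defers to the exclusion | None |
| 9.2.1, SUSAR sentence | 24 hours | None |
| 9.3.3, UAR text | 24 hours | None |

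**Step 1: can one event fall under both sets of rules?** Yes. Table 9a makes an unexpected serious adverse reaction a SUSAR whatever organ system or level of care is involved. The 9.3.2 bullets include the same event by type.

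**Step 2: does causality take the event off the list?** Not by any stated test. The bullet on elective hospitalisation for pre-existing conditions has a condition about trial treatment. Two other bullets (other serious events, and death) are tied to the disease, its treatment or its progression. The three bullets at issue have no such wording.

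**Step 3: does 9.2.1 settle it?** No. Its five-day rule depends on a list of expected events in section 9.1. That section holds the definitions and no list. For expectedness of serious reactions, 9.2.1 itself points to Section 8 of the Investigator Brochure.

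**Step 4: how far does the contradiction extend?**

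- Listed and unrelated: five working days, no conflict.
- Listed, suspected to be related, expected: five working days, no conflict with the SUSAR or UAR rules.
- Listed, suspected to be related, unexpected: five working days and 24 hours, in conflict.

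**Step 5: the size of the difference.** For an event that becomes known on a weekday, five working days plus one weekend is 5 + 2 = 7 calendar days, against 1 day: a possible extra delay of 7 − 1 = 6 days, and longer with public holidays.

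**The case against.** The best defence is that 9.3.2, read as a whole, never reaches an event attributed to the trial drug. Its opening sentence describes the listed events as associated with the participants' disease. The sixth bullet refers to any *other* serious event related to the disease or its medication, which implies that the earlier bullets are disease-related too. On that reading a suspected drug reaction is not on the list and stays on 24 hours under 9.3.1. In addition, the SUSAR and UAR rules are unconditional and more specific, so a careful site would follow them. The investigator assesses causality, seriousness and expectedness under 9.2.1, so the site can recognise a SUSAR without waiting for the sponsor.

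Much of this stands. It shows the probable intention, and it rules out saying that the protocol plainly sends suspected drug reactions to the slow route. It does not remove the gap, for three reasons.

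- The opening sentence is a description and sets no test.
- Association with the disease and suspicion of the drug are not exclusive. Table 9b's category of possible relationship expressly allows the patient's clinical condition to have contributed, and in this population that is the realistic case.
- 9.3.1 and the 9.5 notice defer to the list without mentioning SUSARs. The UAR rule helps only in part: Table 9a does not limit UARs to non-serious reactions, but 9.3.1 speaks of unexpected reactions that are not serious.

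The flow chart mentioned in 9.2 is not visible in the text reviewed. It may give the intended order, but the written sections would still disagree.

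**Conclusion.** The protocol gives two deadlines for a listed event that is both suspected to be related and unexpected, and it states no order of precedence. A site that follows 9.3.1 to 9.3.3 could in good faith hold a SUSAR for five working days when 9.2.1 wants it in 24 hours. This should be corrected.

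A reader might infer three stronger points, which the documents do not support:

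- *That every possibly related ICU admission, sepsis or organ failure is wrongly delayed.* Nothing in section 9 requires 24 hours for a listed event that is related but expected. The five-day route for those events is a choice of scope.
- *That the safety tables are affected.* Listed events are still recorded on the SAE form and reported, so the counts of sepsis and organ failure in the SAP tables do not change.
- *That DMC oversight is impaired.* Under 9.4 the DMC receives SAE reports as often as it asks, and thromboembolism and mortality are reported to it as they occur. No effect on its review is shown.

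The documents do not say how often the overlap would arise. Sample size and the efficacy analysis are not involved. The conclusion rests on the written text of section 9 alone.

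**What to change.** Reconcile the passages in the next protocol amendment.

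1. In the lead-in to 9.3.2, add a sentence such as: *This exception does not apply to any event that meets the SUSAR or UAR definition in Table 9a; such events are notified within 24 hours.*
2. Repeat the condition in 9.3.3 and in the 9.5 notice, and check that the flow chart in 9.2 agrees.
3. In 9.2.1, replace the reference to a list in section 9.1 with a reference to 9.3.2, described as the SAEs excluded from expedited notification. Calling it a list of expected events would confuse it with the reference safety information in the Investigator Brochure.

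The cost is a few lines and an update to the SAE form guidance. For SUSARs it adds no duty beyond what 9.2.1 already imposes. Any increase in expedited reports should be small, though that is an assumption because no frequency is given. Unrelated disease events keep the five-day route, so the purpose of 9.3.2 is preserved.

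The sponsor may also choose to move expected but possibly related listed events to 24 hours. That is optional and would bring in more reports, because the threshold for a possible relationship in Table 9b is low.

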9.3.3. Investigator Notification

- The CTU should be notified as soon as possible and within 24 hours of the investigator becoming aware of any SAE that has occurred, unless it has been excluded from expedited reporting.
- The SAE form must be completed by the Investigator (the consultant named on the delegation of responsibilities log who is responsible for the patient's care). In the absence of the Investigator, the form should be completed by a member of the site trial team and sent to CTU. The responsible Investigator should subsequently check, annotate and sign the form and send to the CTU as soon as possible. The initial report must be followed by detailed written reports as appropriate.
- The Investigator must record all SAEs that occur during the trial period on the SAE form. They are required to notify the CTU within five working days of becoming aware of an SAE that has been excluded from expedited reporting.
- The investigator must follow-up all reported SAEs until resolution or the event is considered stable.
- The CTU should be notified within 24 hours of the investigator becoming aware of an UAR that has occurred. The severity of an UAR will be graded by the CTU using MedDra terminology (Medical Dictionary for Regulatory Activities, Version 17.1, September 2014, and as updated from time to time. The Investigator must supply the CTU, REC and relevant NHS Trust R&D with any supplementary information they request.

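### Protocol 9.3.2 ends with a sentence of unclear scope which, read literally, releases unlisted SAEs from recording and so contradicts 9.3.1, 9.3.3 and the 9.5 notification box

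*Protocol*

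**What the plan says.** - **Protocol 9.1** makes unexpected adverse reactions and SAEs reportable, apart from those already listed as primary or secondary outcomes. It says that other adverse events need not be recorded.
- **Protocol 9.2.1**, under Seriousness, gives two routes. A serious event that "is on the list of expected events in section 9.1" goes on the SAE form within five working days. For the second route: "If the event is a SUSAR it must be recorded on the SAE form and sent to the CTU within 24 hours".
- **Protocol 9.3.1** says that SAEs, related or not, and unexpected non-serious reactions "must be reported within 24 hours of the PI becoming aware of the event, unless they have been specifically excluded from expedited reporting".
- **Protocol 9.3.2** introduces its seven bullets by saying that "the following situations that fulfil the definition of an SAE are excluded from expedited notification, but should be recorded on the SAE form", with five working days allowed. The subsection then ends: "Any event that does not meet the above definitions does not need to be recorded at all".
- **Protocol 9.3.3** follows directly. It asks for notification "within 24 hours of the investigator becoming aware of any SAE that has occurred, unless it has been excluded from expedited reporting", and adds: "The Investigator must record all SAEs that occur during the trial period on the SAE form". It also repeats the 24-hour limit for unexpected adverse reactions.
- **The notification box in Protocol 9.5** restates the 24-hour limit with the same exception.

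**The concern.** The closing sentence of 9.3.2 is an operative instruction about what a site may leave unrecorded. The nearest thing above it that an event could meet or fail to meet is the five-working-day list. Taken that way, it exempts from recording the SAEs for which the neighbouring sections set the tightest deadline.

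Recorded SAEs feed three things:

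- The number of SAEs to day 60 is a secondary safety outcome (Protocol 7.2.2) and is summarised by arm per day at risk (SAP 4.4).
- SAE reports go to the DMC as listings (Protocol 9.4), and an SAE summary by arm goes to it at the interim analysis (SAP 4.1).
- The SAP's interim and final safety tables have a row for other SAEs, so the analysis expects events outside the named categories.

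SAP 4.8 expects safety outcomes to be fully reported, except for participants withdrawn or lost, and does not impute secondary outcomes. An SAE that was never written down is therefore not recoverable in the analysis.

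**Working it through.** No arithmetic applies, because the plan gives no figure on this point. The check is to take each class of event through the sections in turn, reading the 9.3.2 sentence literally against the list above it.

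| Event | 9.1 | 9.2.1 | 9.3.1 | Last sentence of 9.3.2, literal | 9.3.3 and 9.5 box |
|---|---|---|---|---|---|
| SAE on the seven-item list | reportable | five working days (list wrongly located) | excepted from 24 hours | recorded | five working days |
| SUSAR off the list | reportable | 24 hours | 24 hours | not recorded | 24 hours |
| Other SAE off the list, not an outcome | reportable | no route given | 24 hours | **not recorded** | recorded, 24 hours |
| Unexpected reaction, not serious | reportable | not addressed under Seriousness | 24 hours | not recorded | 24 hours (9.3.3) |
| Any other adverse event | not recorded | – | – | not recorded | – |

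On this reading the sentence conflicts with its neighbours in rows 2 to 4. SUSARs and unexpected reactions are protected by explicit 24-hour rules of their own. Row 3 is the most exposed: 9.2.1 has no route for a serious event that is neither listed nor a SUSAR, and the next text such a reader meets in 9.3.2 says that it need not be recorded. Examples are an unlisted SAE unrelated to treatment, or an expected serious reaction. A seizure would be one if the reference safety information lists it as expected. That information is in the Investigator Brochure, which is not part of these documents.

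Now the alternative reading. Suppose that the definitions meant are those of SAE and unexpected adverse reaction in Table 9a, or the categories of 9.3.1 and 9.3.2 together. Only the last row is then exempt, and every column agrees. The wording still does not deliver this by itself:

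- Table 9a also defines an adverse event, as any untoward medical occurrence in a participant. If the whole table is meant, every event meets a definition and the sentence exempts nothing. The reader has to limit it, unprompted, to the SAE and unexpected-reaction rows.
- 9.3.1 is a reporting rule and defines nothing.
- On this reading the sentence only repeats 9.1, so nothing is lost by removing it.

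On the cross-reference: 9.1 contains the definitions in Table 9a but no list of expected events. The five-working-day list is in 9.3.2.

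On the effect of omission: let L and U be the listed and the exposed unlisted SAEs in an arm. Full adherence to the literal reading records L instead of L + U. If treatment shifts L and U in the same proportion, the ratio between arms is unchanged and the absolute difference shrinks by the factor L/(L + U). If a treatment effect falls mainly on U, the ratio moves towards 1 as well. The documents give neither L nor U.

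**The case against.** The strongest counter-case is that the benign reading is available and fits the rest of the section. 9.3.2 calls its bullets situations and uses the word definition only for the definition of an SAE. Table 9a is itself titled as definitions, and 9.1 has a parallel sentence whose scope is clear. The literal reading would also leave the SAE part of 9.3.1 with nothing to report. A reader might infer that 9.3.2 reverses the 24-hour rule. The documents do not support that: 9.3.3 restates the rule immediately afterwards, together with the duty to record all SAEs, and the 9.5 box states it again.

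The reach is also limited:

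- SUSARs and unexpected reactions have their own rules.
- Thrombotic events and veno-occlusive disease have a separate form (SAP Table 1, Form 19).
- The seven items include major organ dysfunction, and a catch-all for serious events related to the disease or its treatment. A serious renal event, for example, could well be listed.
- Treatment is double-blind and randomisation is stratified by site, so a misreading by a whole site would not be expected to differ by arm.
- Section 9.2 refers sites to a flow chart, which is not in the text available for this review and may point the right way.

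All of this stands and limits the finding. It does not remove the conflict. The benign reading has to be supplied by the reader, and 9.2.1 sends that reader to a list in the wrong section. Balance between arms would also not restore lost counts in a trial that already acknowledges low power to detect increased thromboembolic rates.

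**Conclusion.** The sentence is ambiguous, and on its most natural reading in place it contradicts 9.3.1, 9.3.3 and the 9.5 box. This is an internal inconsistency in a safety-recording instruction, not a fault in the design. It should be corrected.

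The events most at risk are SAEs that are off the seven-item list, are not SUSARs and are not already captured as outcomes. They could be missing from the day-60 SAE count and the DMC listings at any site that followed the literal reading. The size cannot be derived from the documents. It depends on how sites read the sentence and on how many SAEs fall in that class, and neither is given.

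A reader might go further and infer that SAEs were in fact under-recorded, or that drug-related events in general escape reporting. The documents support neither: there is no evidence of site behaviour, and unexpected reactions, serious or not, keep an explicit 24-hour rule.

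**What to change.** 1. Delete the last sentence of 9.3.2 and rely on 9.1. Alternatively, replace it with: *Adverse events that are neither SAEs nor unexpected adverse reactions need not be recorded (Section 9.1). SAEs not listed above, and not already captured as primary or secondary outcomes under Section 9.1, are recorded and reported within 24 hours (Sections 9.3.1 and 9.3.3).* The reference to outcomes matters. Without it, the new text could pull bleeding and thrombotic outcomes into 24-hour SAE reporting and create a fresh conflict with 9.1.
2. In 9.2.1, change the cross-reference for the five-working-day list from 9.1 to 9.3.2.
3. Tell sites which reading applies.

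The cost is two text edits in an amendment and a note to sites. The outcomes, the analysis and the sample size are unaffected.
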